2.6.2 Statistical hypothesis, model, and method of analysis

PFS

PFS will not be analyzed due to the permanent halt of recruitment and early termination of study.

ORR/CBR

Overall responses data will be listed.

ECOG performance status

ECOG data will be listed by treatment group and assessment time point.

2.7 Safety analyses

For all safety analyses, the safety set will be used. All listings and tables will be presented by treatment group.

Safety summaries (tables, figures) include only data from the on-treatment period with the exception of baseline data which will also be summarized where appropriate (e.g. change from baseline summaries). In addition, a separate summary for deaths including on treatment and post treatment deaths will be provided.

The on-treatment period lasts from the date of first administration of study treatment to 30 days after the date of the last actual administration of any study treatment.

The overall observation period will be divided into three mutually exclusive segments:

1. Pre-treatment period: from day of participant's informed consent to the day before first dose of study treatment
2. On-treatment period: from day of first dose of study treatment to 30 days after last dose of study treatment
3. Post-treatment period: starting at day 31 after last dose of study treatment.

2.7.1 Adverse events (AEs)

Summary tables for adverse events (AEs) will include only AEs that started or worsened during the on-treatment period, the treatment-emergent AEs. However, all safety data (including those from the pre and post-treatment periods) will be listed and those collected during the pre-treatment and post-treatment period are to be flagged. All information obtained on adverse events will be displayed by treatment group.

The number (and percentage) of participants with treatment emergent adverse events will be summarized by treatment, system organ class, preferred term and maximum severity. A participant with multiple grades for an AE will be summarized under the maximum grade recorded for the event. AEs with a missing CTCAE grade will be included in the 'All grades' column of the summary tables.

A participant with multiple adverse events within a system organ class is only counted once towards the total of the system organ class.

Separate summaries will be provided for serious adverse events if there are serious adverse events reported.

In AE summaries the system organ class will be presented alphabetically and the preferred terms will be sorted within SOC in descending frequency. The sort order for the preferred term will be based on their frequency in the dapagliflozin plus metformin XR treatment group.

The frequency of grade 3 and above AEs will be summarized separately.

All AEs, deaths, and serious adverse events (including those from the pre and post-treatment periods) will be listed by treatment group and those collected during the pre-treatment and post-treatment period will be flagged.

2.7.2 Clinical trial safety disclosure

For the legal requirements of ClinicalTrials.gov and EudraCT, two required tables adverse events which are not serious adverse events and serious adverse events and SAE suspected to be related to study treatment will be provided by system organ class and preferred term on the safety set.

If for the same patient, several consecutive AEs (irrespective of study treatment causality, seriousness and severity) occurred with the same SOC and PT:

- a single occurrence will be counted if there is ≤ 1 day gap between the end date of the preceding AE and the start date of the consecutive AE
- more than one occurrence will be counted if there is > 1 day gap between the end date of the preceding AE and the start date of the consecutive AE

For occurrence, the presence of at least one SAE / SAE suspected to be related to study treatment / non SAE has to be checked in a block e.g., among AE's in a ≤ 1 day gap block, if at least one SAE is occurring, then one occurrence is calculated for that SAE.

The number of deaths resulting from SAEs suspected to be related to study treatment and SAEs irrespective of study treatment relationship will be provided by SOC and PT.

2.7.3 Deaths

All deaths will be listed, post treatment deaths will be flagged.

2.7.4 Laboratory data

Regarding laboratory assessments, data from all sources (central and local laboratories) will be combined. Listing of participants with CTC grade 3 or 4 laboratory abnormalities will be provided.

Liver function parameters

Liver function parameters of interest in this study are total bilirubin (TBIL), ALT, AST and alkaline phosphatase (ALP).

The participants meeting the following categorical liver function test criteria will be listed:

- ALT > 3xULN, 5xULN, 10xULN, 20xULN
- AST > 3xULN, 5xULN, 10xULN, 20xULN
- ALP > 1.5xULN
- ALT or AST > 3xULN, 5xULN, 8xULN, 10xULN, 20xULN
- TBIL > 2xULN, 3xULN

For the following combined categories (the assessments need not be concurrent, i.e. participants are counted based on their most extreme value for each parameter. Further medical review can assess potential confounding factors such as, liver metastases, liver function at baseline etc.

- If AST and ALT \leq ULN at baseline
 - ALT or AST > 3x ULN & TBIL > 2x ULN
 - ALT or AST > 3x ULN & TBIL > 2x ULN & ALP \geq 2x ULN
 - ALT or AST > 3x ULN & TBIL > 2x ULN & ALP < 2x ULN
- If AST and ALT > ULN at baseline
 - Elevated ALT or AST (> 3x Baseline value or 8x ULN) & TBIL (> 2x Baseline value and 2x ULN)
 - Elevated ALT or AST (> 3x Baseline value or 8x ULN) & TBIL (> 2x Baseline value and 2x ULN) & ALP \geq 2x ULN
 - Elevated ALT or AST (> 3x Baseline value or 8x ULN) & TBIL (> 2x Baseline value and 2x ULN) & ALP < 2x ULN

Additional categories may be added to the above list based on any updates to the internal guidelines on collection, analysis, and presentation of liver safety data.

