  - Calcium (corrected for serum albumin) and magnesium within normal limits or  $\leq$  grade 1 according to National Cancer Institute (NCI) - Common Terminology Criteria for Adverse Events (CTCAE) version 4.03 if judged clinically not significant by the Investigator
  - Potassium within normal limits, or corrected with supplements
  - International Normalized Ratio (INR)  $\leq 1.5$
  - Total bilirubin  $< 2 \times$  upper limit of normal (ULN) (any elevated bilirubin should be asymptomatic at enrollment) except for participants with Gilbert's syndrome who may only be included if the total bilirubin is  $\leq 3.0 \times$  ULN or direct bilirubin  $\leq 1.5 \times$  ULN
  - In absence of liver metastases, alanine aminotransferase (ALT) and aspartate aminotransferase (AST)  $< 3 \times$  ULN. If the participant has liver metastases, ALT and AST  $\leq 5 \times$  ULN, he/she will be eligible for the study
  - Fasting Serum amylase  $\leq 2 \times$  ULN
  - Fasting Serum lipase  $\leq$  ULN

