For participants with normal ALT and AST and total bilirubin value at baseline: AST or ALT > 3.0 x upper limit of normal (ULN) combined with total bilirubin > 2.0 x ULN without evidence of cholestasis  For participants with elevated AST or ALT or total bilirubin value at baseline: [AST or ALT > 3.0 x baseline] or [ALT or AST > 8.0 x ULN], whichever occurs first, combined with [total bilirubin > 2.0 x baseline AND > 2.0 x ULN]  Note: For participants with Gilbert's syndrome, at least 2-fold increase in direct bilirubin.	
 
Interrupt treatment and adjudicate for DILI: Repeat as soon as possible, preferably within 48 hours from awareness of the abnormal results, then with weekly monitoring of LFTsb, or as clinically indicated, until AST, ALT, or total bilirubin have resolved ≤ ULN or to baseline. (Refer to the Section 6.6.3.1 for additional follow-up evaluations as applicable.) 
 
If causality assessment indicates that DILI is probable: Permanently discontinue participant from treatment.
 
If not DILI: Treat the identified cause according to institutional guidelines. Once resolved, reduce by one dose level.
 
 
 

Gastrointestinal	
Diarrhea is defined as: a disorder characterized by frequent and watery bowel movements.	
Grade 1 (Increase of < 4 stools per day over baseline; mild increase in ostomy output compared to baseline)	
 
Maintain dose level but initiate appropriate medical therapy and monitor as clinically indicated.
 

Grade 2 (Increase of 4 - 6 stools per day over baseline; moderate increase in ostomy output compared to baseline; limiting instrumental Activities of Daily Living (ADL))	
 
Omit dose until resolved to ≤ Grade 1, then restart at same dose.
 
If diarrhea returns as ≥ Grade 2, then omit dose until resolved to ≤ Grade 1, then decrease 1 dose level
 
Initiate or intensify appropriate medical therapy and monitor as clinically indicated.
 

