Following appropriate causality assessments, as outlined above, the causality of the treatment is estimated as "probable" i.e. > 50% likely, if it appears greater than all other possible causes of liver injury combined. The term "treatment-induced" indicates probably caused by the treatment, not by something else, and only such a case can be considered a DILI case and should be reported as an SAE.

All cases confirmed on repeat testing meeting the laboratory criteria defined above, with no other alternative cause for LFT abnormalities identified, should be considered as "medically significant," and thus, meet the definition of SAE and should be reported as SAE using the term "potential treatment-induced liver injury." All events should be followed up with the outcome clearly documented.

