## 16 Appendices

### 16.1 Appendix 1: Liver event and laboratory trigger definitions & follow-up requirements

**Table 16-1 Liver event and laboratory trigger definitions**

	Definition/ threshold
Liver laboratory triggers If ALT, AST and total bilirubin normal at baseline:	
 
• ALT or AST <math>> 5 \times</math> ULN
 
• ALP <math>> 2 \times</math> ULN (in the absence of known bone pathology)
 
• Total bilirubin <math>> 3 \times</math> ULN (in the absence of known Gilbert syndrome)
 
• ALT or AST <math>> 3 \times</math> ULN and INR <math>> 1.5</math>
 
• Potential Hy's Law cases (defined as ALT or AST <math>> 3 \times</math> ULN and Total bilirubin <math>> 2 \times</math> ULN [mainly conjugated fraction] without notable increase in ALP to <math>> 2 \times</math> ULN)
 
• Any clinical event of jaundice (or equivalent term)
 
• ALT or AST <math>> 3 \times</math> ULN accompanied by (general) malaise, fatigue, abdominal pain, nausea, or vomiting, or rash with eosinophilia
 
• Any adverse event potentially indicative of a liver toxicity
 

If ALT or AST abnormal at baseline:	
 
• ALT or AST <math>> 3 \times</math> baseline or <math>> 300</math> U/L (whichever occurs first)
 

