3.1 Primary endpoint(s)

The sample size calculation is based on the primary endpoint occurrence of severe hyperglycemia. The hypotheses to be tested and details of the testing strategy are described in [Section 2.5.2](#).

The incidence of severe hyperglycemia adverse events over the first eight weeks of alpelisib plus fulvestrant treatment in the study treatment arm B (i.e. prophylactic metformin XR alone) is assumed to be 40% based on data from the SOLAR-1 study in HR-positive, HER2-negative, advanced breast cancer participants with a PIK3CA mutation treated with alpelisib plus fulvestrant.

It is expected that treatment with prophylactic dapagliflozin plus metformin XR will result in a 20% reduction in the incidence rate. Approximately 124 participants (62 in each arm) will be required to detect a 20% difference in incidence rate with 80% power using the difference of proportion test at a one-sided 5% level of significance ([Table 3-1](#)). Assuming a 5% dropout rate (participants without adequate assessment of glucose laboratory values per protocol from Cycle 1 Day 8 to Cycle 3 Day 8) at the time of primary analysis, approximately 132 participants will need to be randomized to the two treatment arms in a 1:1 fashion.

Table 3-1 Sensitivity of power to changes in assumptions for N=124

Expected reduction in incidence rate	Observed reduction in incidence rate	Power
20%	30%	99.2%
	25%	93.8%
	20%	79.1%
	15%	56.1%
	10%	32.0%
	5%	14.2%

Note: Simulations are performed in East 6.4 with number of simulations = 100,000 and randomization seed = 2020.

4 Change to protocol specified analyses

Due to the permanent halt of recruitment and early termination of study, the primary analysis will not be conducted. Instead,

- the primary endpoint will only be summarized descriptively without any supplementary analysis.
- the secondary efficacy endpoint, PFS will only be listed without summaries.
- the secondary efficacy endpoints ORR and CBR will only be listed without summaries.
- there will be no subgroup analyses for efficacy and safety endpoints
- the study treatment such as exposure and dose intensity will only be listed without summaries.
- for safety endpoints, only adverse events, deaths and serious adverse events will be summarized. Other safety endpoints will only be listed for participants with notable values.

5 Appendix

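### SAP 2.7.4 sorts the combined ALT/AST plus bilirubin categories under two baseline headings that are not complementary, so a participant with exactly one raised transaminase at baseline fits none of them.

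*SAP*

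**What the plan says.** SAP Section 2.7.4 (Liver function parameters) first names single-parameter criteria with no baseline condition, for example "ALT or AST > 3xULN, 5xULN, 8xULN, 10xULN, 20xULN" and TBIL above 2 or 3 x ULN. It then gives six combined categories under two baseline headings. The first requires both AST and ALT to be at or below ULN. The second reads "If AST and ALT > ULN at baseline". Under it, a case needs ALT or AST above 3 x baseline or 8 x ULN, together with TBIL above 2 x baseline and 2 x ULN, with further categories split by ALP at 2 x ULN.

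Protocol Table 6-3 and Section 6.6.3.1 use the same transaminase and bilirubin multiples to define potential drug-induced liver injury (DILI), but word the elevated-baseline group differently: "For participants with elevated AST or ALT or total bilirubin value at baseline". The other protocol group requires all three to be normal. Protocol Table 16-1 also joins the two enzymes with *or*: "If ALT or AST abnormal at baseline".

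On eligibility, Protocol Section 5.1 requires ALT and AST below 3 x ULN. For a participant with liver metastases the limit is relaxed ("If the participant has liver metastases, ALT and AST" up to 5 x ULN). Total bilirubin must be below 2 x ULN, with an exception for Gilbert's syndrome. Nothing requires the two enzymes to be both normal or both raised.

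**The concern.** Both SAP headings join the enzymes with *and*, so they describe the two extreme patterns and skip the mixed ones. This cannot be put down to loose usage, because the same list writes *or* wherever either enzyme is enough. A programmer who codes the second heading as it stands will leave participants with one raised transaminase out of all six combined categories.

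The combined pattern is the reason these categories exist: Protocol Section 6.6.3.1 treats a transaminase rise together with a bilirubin rise as possibly indicating severe DILI. It also matters that the study was stopped early. SAP Section 4 reduces the remaining safety output to listings ("Other safety endpoints will only be listed for participants with notable values"), so the stated criteria decide who is identified. What would be lost is recognition of the combined pattern in the liver output, not the underlying data.

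**Working it through.** There is no planned figure to reproduce. The check is an enumeration of baseline patterns followed by two worked cases.

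**Enumeration.** Each of AST, ALT and TBIL is at or below ULN (N) or above ULN (H) at baseline, giving 2 x 2 x 2 = 8 patterns. Each is assigned using the SAP headings, the protocol groups (Table 6-3 and Section 6.6.3.1), and the SAP headings with *or* in the second.

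| AST | ALT | TBIL | SAP as written | Protocol | SAP with *or* |
|---|---|---|---|---|---|
| N | N | N | normal | normal | normal |
| N | N | H | normal | elevated | normal |
| N | H | N | **none** | elevated | elevated |
| N | H | H | **none** | elevated | elevated |
| H | N | N | **none** | elevated | elevated |
| H | N | H | **none** | elevated | elevated |
| H | H | N | elevated | elevated | elevated |
| H | H | H | elevated | elevated | elevated |

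- SAP as written: 2 + 2 = 4 patterns covered, 8 - 4 = 4 uncovered. On AST and ALT alone, 2 of 4 are uncovered.
- Protocol: 1 + 7 = 8 covered, 0 uncovered.
- SAP with *or*: 2 + 6 = 8 covered, each exactly once. One pattern (normal AST and ALT, raised TBIL) is still grouped differently from the protocol.

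**Case 1 (illustrative values, in multiples of ULN).** Baseline ALT 1.2, AST normal, TBIL 0.8. Peak ALT 4, peak TBIL 2.5.

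- ALT: 3 x 1.2 = 3.6, and 4 > 3.6.
- TBIL: 2 x 0.8 = 1.6, and 2.5 exceeds both 1.6 and 2.
- The protocol's elevated-baseline criterion is met. No SAP heading applies, so no combined category does.
- By the SAP Section 5.3 grading table, ALT at 4 x ULN (above 3 to 5) and TBIL at 2.5 x ULN (above 1.5 to 3) are both grade 2, so the grade 3 or 4 listing also misses the case. It appears only in the separate listings for ALT above 3 x ULN and TBIL above 2 x ULN.
- With the same peaks, the participant would have been captured under the first heading had baseline ALT been normal, or under the second had AST also been raised.

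**Case 2 (illustrative).** ALT raised at baseline, AST 0.5 rising to 1.8, and TBIL meeting its condition as in Case 1.

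- AST: 3 x 0.5 = 1.5, and 1.8 > 1.5, so the protocol's transaminase condition is met.
- AST at 1.8 is below 3 x ULN, so it reaches no single-parameter transaminase listing. Unless ALT itself passes 3 x ULN, the case shows only under TBIL above 2 x ULN.

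**The case against.** The gap on the literal text is not in dispute; the argument is about its weight.

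- *Nobody disappears from the liver output.* The protocol's elevated-baseline criterion requires TBIL above 2 x ULN, so every affected participant is in the TBIL listing. This stands. The transaminase value, however, is not guaranteed to be listed (Case 2), and neither the joint pattern nor the ALP split is shown.
- *The output is descriptive and no conclusion depends on it.* This stands, and it limits the severity.
- *Participant protection runs on the protocol, whose criteria are exhaustive.* This also stands. "All cases confirmed on repeat testing meeting the laboratory criteria defined above", with no other cause found, are reported as SAEs. That route is filtered by causality, though, whereas the SAP categories rest on laboratory values alone.
- *The SAP was not meant to copy the protocol criterion.* Partly right. The SAP uses non-concurrent worst values and splits by ALP, and the protocol's normal-baseline group adds the absence of cholestasis. Protocol Section 12.5.2 specifies no combined liver analysis, so the silence of SAP Section 4 on this point carries little weight. The multiples do match, and neither document gives a reason to drop mixed baselines.
- *It is probably a drafting slip, and the programming specification may already be right.* Possibly, but that specification is not among the documents. The SAP's allowance for additional categories depends on updates to internal guidelines, and its reference to medical review concerns confounders. Neither assigns an omitted participant to a category.

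**Conclusion.** The point holds. As written, SAP Section 2.7.4 leaves 2 of 4 AST/ALT baseline patterns, or 4 of 8 with TBIL, outside every combined category, against 0 of 8 under the protocol's grouping. These are counts of logical patterns, not a share of participants. The number affected cannot be derived, because no baseline distribution is given and recruitment was halted; it may be zero. The conclusion assumes only that the heading is programmed as worded and that a participant with one raised transaminase can be enrolled, which Protocol Section 5.1 allows. The consequence is an incomplete combined-pattern listing, with no effect on any test, estimate or on collected data. It should be corrected, but it is not a critical flaw.

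**What to change.** Reword the second baseline heading in SAP Section 2.7.4 to AST or ALT > ULN at baseline, and make the same change in the programming condition. All 8 patterns are then covered exactly once. The cost is one word and one line of code, with no new data or analysis.

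Separately, decide whether baseline TBIL should also determine the group, as it does in Protocol Table 6-3 and Section 6.6.3.1. After the change, normal AST and ALT with raised TBIL (1 of 8 patterns) is the only pattern the two documents group differently. They should be reconciled or the difference explained, but this is not needed to close the gap described here.

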2.7.5 Other safety data

2.7.5.1 ECG

A listing of participants with notable ECG values will be listed by treatment group as defined in [Table 2-5](#). Notable elevations include only newly occurring ECG. A newly occurring ECG abnormality is defined as an abnormal post-baseline ECG finding that is not present at Baseline.

Table 2-5 Clinically notable ECG values

ECG parameter (unit)	Clinically notable criteria
QT, QTcF (ms)	New > 450 and \leq 480 New > 480 and \leq 500 New > 500 Increase from Baseline > 30 to \leq 60 Increase from Baseline > 60
PR duration (ms)	Increase from baseline > 25% and to a value > 200 New > 200
QRS duration (ms)	Increase from baseline > 25% and to a value > 120 New > 120
Heart Rate (bpm)	< 50 and decrease from Baseline of > 25%

> 100 and increase from Baseline of > 25%

2.7.5.2 Cardiac imaging

A listing of participants with newly occurring clinically significant abnormality will be produced by treatment group.

2.7.5.3 Vital signs

Vital signs assessments are performed in order to characterize basic body function. The parameters expected to be collected include: weight, body temperature, pulse rate, and systolic and diastolic blood pressure.

The criteria for clinically notable abnormalities are defined in [Table 2-6](#) below.

Table 2-6 Clinically notable changes in vital signs

[figure not shown]
Vital sign (unit)	Clinically notable criteria	
	above normal value	below normal value
Systolic blood pressure (mmHg)	≥180 with increase from baseline of ≥20	≤90 with decrease from baseline of ≥20
Diastolic blood pressure (mmHg)	≥105 with increase from baseline of ≥15	≤50 with decrease from baseline of ≥15
Pulse rate (bpm)	≥100 with increase from baseline of >25%	≤50 with decrease from baseline of > 25%
Body temperature	≥ 39.1	-
Weight (kg)	increase ≥ 10% from Baseline	decrease ≥ 10% from Baseline

Participants with clinically notable vital sign abnormalities will be listed by treatment group. In the listing, the clinically notable values will be flagged and also assessments collected later than 30 days after the last treatment date will be flagged.

2.7.5.4 Other

Data with notable values from other tests will be listed as appropriate.

All assessments collected later than 30 days after the last treatment date will be flagged in the listings.

2.8.2 Duration of follow-up

Study follow-up will be summarized using the following methods:

- Summary of duration between randomization and cut-off date, which are defined as follows:
 - Randomization (recruitment) period = (Date of last participant randomized - Date of first participant randomized + 1) / 30.4375 (months)
 - Duration between randomization and data cut-off date = (Cut-off date – Date of randomization + 1) / 30.4375 (months). This item will be summarized overall.

All summaries will be reported in months.

